4.4. Secondary Endpoint Analysis

Endpoints for secondary objectives will be evaluated based on the primary efficacy estimand. Missing data will be addressed by the MMRM model.

4.4.1. Definition of endpoints

The following secondary endpoints are defined:

- Change from baseline in %TAR:
 - Change from baseline to Week 12 in percentage of time per day that CGM-derived values are >180 mg/dl (10 mmol/L)
 - Percentage of time above range for a given day will be calculated as 100 times the number of CGM readings where a participant's blood glucose falls above the specified range during a day (00:00 to 23:59, inclusive), divided by the total number of CGM readings in the time interval (00:00 to 23:59, inclusive). This will be averaged over the days from Day 1 to Day 14 to obtain the %TAR for a participant.
- Change from baseline in TAR:
 - Changed from baseline to Week 12 in duration of time in minutes per day that CGMderived values are >180 mg/dl (10 mmol/L)
 - Duration of time in minutes will be calculated as the percentage of time above range (%TAR) multiplied by the length of the time period (1440 minutes).
- Change from baseline to Week 12 in Fasting Serum Glucose (FSG)
- Change from baseline to Week 12 in weight

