1.1. Objectives, Endpoints, and Estimands

Objectives	Endpoints
Primary	
• To demonstrate that participants with T2D switching from a stable dose of GLP-1 RA to tirzepatide 5 mg QW have an improvement in HbA1c at Week 12 compared to baseline	• Change from baseline in HbA1c
Secondary	
 To evaluate the changes in CGM- assessed TAR from baseline at Week 4 and at Week 12 	 Change from baseline in Percentage of time per day that CGM-derived values are >180 mg/dl (10 mmol/L) Duration of time in minutes per day that CGM-derived values are >180 mg/dl (10 mmol/L)
• To evaluate the change in FSG from baseline at Week 12	• Change from baseline in FSG
• To evaluate the changes from baseline in weight at Week 12	• Change from baseline in weight
Exploratory	

• To evaluate changes in CCM derived	Change from baseline in
• To evaluate changes in COM-derived	
measures from baseline over the	 standard CGM metrics (TIR,
course of 12 weeks	TBR, GV)
	 time in TITR
	 composite of all in-ranges
	 mean 24-hr daily blood
	glucose
	 estimated post-prandial
	glucose excursion
	 estimated fasting glucose
Abbreviations:	

 $CGM = continuous glucose monitoring; FSG = fasting serum glucose; GLP-1 RA = glucagon-like peptide-1 receptor agonist; GV = glycemic variability; HbA1c = hemoglobin A1c; QW = once-weekly; T2D = type-2 diabetes; TAR = time above range (>180 mg/dl or >10 mmol/L); TBR = time below range (<math>\leq$ 70 mg/dl or \leq 3.9 mmol/L); TIR = time-in-range (71 to 180 mg/dL or 3.9 to 10 mmol/L); TITR = time in tight target range (71 to 140 mg/dL or 3.9 to 7.8 mmol/L);

Primary estimand

The primary estimand in this study is the efficacy estimand.

The efficacy estimand focuses on the treatment effect if participants continued to receive the study treatment without prohibited medication. This estimand will be used in publications to inform prescribers or physicians.

The primary clinical question of interest is

What is the change in HbA1c from baseline to Week 12 in participants with T2D, regardless of changes in background oral antihyperglycemic medication (OAM), and assuming that participants continue to take treatment without use of prohibited medication?

This estimand is described by the following attributes:

- Population: participants with T2D on a GLP-1 RA who may benefit from additional therapy. Further details can be found in Protocol Section 5.
- Endpoint: changes from baseline to Week 12 in HbA1c.

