$$SD_b = \sqrt{\frac{\sum_{j=1}^m \left(\overline{BG_j} - \frac{\sum_{j=1}^m \overline{BG_j}}{m}\right)^2}{m-1}}$$

- Calculated as glucose coefficient of variation (CV):
 - Within-day $CV(CV_w)$

Each participant should have one CV_w per CGM session. CV_w is calculated by calculating the CV individually on all valid days withing a CGM session and then averaging those CVs across all days in the session:

$$CV_w = \frac{\sum_{j=1}^m CV_j}{m}$$

where m stands for the number of valid CGM days in a session and

$$CV_j = \frac{SD_j}{\overline{BG_j}} \times 100$$

• Between-day $CV(CV_b)$

Each participant should have one CV_b per CGM session. CV_b is calculated by averaging the glucose values individually on each valid day within a session and then calculating the CV across those days:

$$CV_b = \left| \frac{SD_b}{\underline{\sum_{j=1}^m \overline{BG_j}}} \right| \times 100$$

- TITR Time in Tight Target Range (71 to 140 mg/dL or 3.9 to 7.8 mmol/L)
 - Calculated as percentage of time per day in tight target range:
 - Percentage of time in tight target range for a given day will be calculated as 100 times the number of CGM data readings where a participant's blood glucose falls within the specified range during a day (00:00 to 23:59, inclusive), divided by the total number of readings in the time interval (00:00 to 23:59, inclusive). This will be averaged over the days from Day 1 to Day 14 to obtain TITR for a participant at a visit.
- Composite of all in ranges
 - Composite endpoint of the recommended time in all three International CGM Consensus Guidelines ranges (<4% in TBR [≤70 mg/dL], >70% in TIR, and <25% in TAR [>180 mg/dL]):

- A binary endpoint will be created. If for a participant at a visit all three CGM measures (TAR, TIR, TBR) are within the recommended time-ranges then the composite endpoint will be set to "Y" for that participant, otherwise it will be set to "N".
- Mean 24-hr daily blood glucose

Calculated by averaging all non-missing glucose readings a day (00:00 to 23:59, inclusive) and averaging across the 14 days to obtain mean daily glucose for a participant at a visit.

• Fasting glucose and post-prandial glucose excursion

Both the endpoints are algorithmically derived from the entire CGM dataset. An algorithm reviews the entire CGM dataset, evaluates excursions, and time periods then estimates either the fasting glucose or post-prandial glucose excursion.

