4.9. Changes to Protocol-Planned Analyses

There are no changes to protocol planned analyses.

5. Sample Size Determination

A sample size of 150 participants will provide at least 90% power to show an improvement in HbA1c from baseline at Week 12. This sample size is using the following assumptions:

- a 1-sample t-test with 2-sided significance level of 0.05
- within treatment difference from baseline at Week 12 is 0.3%, and
- intra-subject variability of 1.1%.

6. Supporting Documentation

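### The SAP's conversion from %TAR to minutes per day omits the division by 100, so the rule as written gives values 100 times too large

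*SAP*

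**What the plan says.** Time above range (TAR) enters the secondary objectives as two endpoints: the percentage of the day above 180 mg/dL, and the time itself, "Duration of time in minutes per day that CGM-derived values are >180 mg/dl (10 mmol/L" (SAP Section 1.1). The protocol's synopsis and objectives table name the same two endpoints but give no formula for either.

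The derivations are in SAP Section 4.4.1:

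- Daily %TAR is "100 times the number of CGM readings where a participant's blood glucose falls above the specified range during a day", "divided by the total number of CGM readings in the time interval (00:00 to 23:59, inclusive".
- Participant-level %TAR is a plain mean of the daily values: "This will be averaged over the days from Day 1 to Day 14 to obtain the %TAR for a participant".
- Minutes per day are then "calculated as the percentage of time above range (%TAR) multiplied by the length of the time period (1440 minutes".

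SAP Section 4.4.2 (Table 2) analyses %TAR and TAR in minutes as separate variables, each with its own MMRM and its own baseline covariate.

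**The concern.** The factor of 100 is built into %TAR when that variable is created, and the minutes line uses the same variable by name. Nothing between the two turns it back into a proportion. The product is therefore percentage points times minutes, whereas the endpoint is defined in minutes per day and cannot leave the range 0 to 1,440.

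This line is the only derivation of a prespecified secondary endpoint in either document, so it is the text a programmer would code from and a validator would check against. At stake is the size of the reported minutes: their descriptive statistics, LS means and confidence limits.

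**Working it through.** **Inputs (SAP Section 4.4.1).** Daily %TAR = 100 × (readings above range / total readings). The ratio lies between 0 and 1, so daily %TAR lies between 0 and 100. Averaging over Days 1 to 14 keeps that scale. The period is 1440 minutes.

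**The plan's own figure.** 00:00 to 23:59 inclusive is 24 × 60 = 1,440 minutes. The stated period is right.

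**Scale used elsewhere.** The composite endpoint in SAP Section 4.5 sets its threshold as "<25% in TAR [>180 mg/dL", which confirms that the SAP expresses this measure in percent.

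**Rule as written and rule with the division.**

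| %TAR | %TAR × 1440 | (%TAR / 100) × 1440 |
|---|---|---|
| 0 | 0 | 0 |
| 0.5 | 720 | 7.2 |
| 1 | 1,440 | 14.4 |
| 10 | 14,400 | 144 |
| 25 | 36,000 | 360 |
| 50 | 72,000 | 720 |
| 100 | 144,000 | 1,440 |

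Each non-zero entry in the middle column is exactly 100 times the entry to its right. The middle column reaches the length of a day at %TAR = 1 and exceeds it for anything higher. Changes scale the same way: a 10-point fall in %TAR reads as 14,400 minutes per day instead of 144.

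**Effect on the analysis.** Write k for the multiplier, 1440 or 14.4. The outcome is k × change in %TAR and the baseline covariate is k × baseline %TAR. Visit and baseline HbA1c category do not involve k. Multiplying outcome and baseline by the same constant multiplies the LS mean, its SE and both confidence limits by k. The ratio LS mean / SE does not depend on k, so the test statistic and P-value are the same for either multiplier, and the interval excludes zero in one case exactly when it does in the other.

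A simple illustration used 150 simulated participants. Its assumptions are not taken from the documents: baseline %TAR from a beta(2, 5) distribution × 100, a fall with mean 8 and SD 12 points, and values limited to 0 to 100. The one-sample t statistic was −5.54 for %TAR, for %TAR × 1440 and for %TAR × 14.4. The mean change was −7,838 with the rule as written and −78.4 with the division.

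**The case against.** The minutes line is prose, not an equation. In ordinary percent arithmetic, 25% multiplied by 1,440 minutes is 360 minutes, and reaching 36,000 means dropping the percent sign. The unit is stated, so impossible values would show at the first output. The %TAR row in the same set of results would expose the mistake, because minutes are a fixed multiple of %TAR.

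Most of this stands, and it limits the severity. It does not make the text correct. The SAP put the 100 into the variable explicitly, and it writes such factors out elsewhere, as in the coefficient-of-variation formulas of Section 4.5. Someone coding from the definitions has to depart from them to get a valid result.

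A reader might infer more than the documents support:

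- **That wrong minutes will be reported.** This cannot be shown. SAP Section 1 places the table, figure and listing specifications in a separate document, which may already have the conversion right. Version 2.0 is described as an update after a dry run; its list of key changes does not mention Section 4.4.1, and the SAP does not say what the dry run covered.
- **That the statistical conclusion on TAR is at risk.** It is not, because a constant multiplier cancels from the test.
- **That literally every value is wrong.** A TAR of zero, or a change of zero, is unaffected.
- **That the error spreads to other endpoints.** The composite takes TAR as a percentage, and neither the HbA1c analysis nor the sample size uses TAR.

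**Conclusion.** The rule for TAR in minutes is wrong as written, by a factor of exactly 100 for every non-zero value. The size follows from the SAP's own definitions and needs no outside figure. The consequence is conditional: only if the line is programmed literally would the mean, SD, LS mean, SE and confidence limits of this one secondary endpoint be inflated 100-fold. Inference on TAR would be intact, and the %TAR endpoint would carry the same information on the correct scale. Severity is minor.

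**What to change.** In SAP Section 4.4.1, replace the minutes derivation with: TAR (min/day) = (%TAR / 100) × 1440 = 14.4 × %TAR, where %TAR is on the 0 to 100 scale.

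Confirm that the output specifications and analysis code use the same expression. Two checks are enough: all participant-level values lie between 0 and 1,440, and the LS mean, SE and confidence limits for minutes equal 14.4 times those for %TAR, apart from rounding.

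The cost is one line of SAP text. Design, data collection, models and tests do not change.

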4.4.2. Main analytical approach

The same analytical approach will be applied for all secondary endpoints as for the primary endpoint, which is detailed under Section 4.3.2.

For secondary endpoints, MMRM will include baseline HbA1c ($\leq 8.0\%$, >8.0%) category as a covariate instead of continuous baseline HbA1c.

Objective	Efficacy Measure	Analysis Conducted	Additional information
CGM parameters	Change from baseline in %TAR at Week 12	MMRM as specified in Section 4.3.2.	 MMRM with terms for: Visits Baseline HbA1c category (≤8.0%, >8.0%) Baseline %TAR
CGM parameters	Change from baseline in TAR at Week 12	MMRM as specified in Section 4.3.2.	 MMRM with terms for: Visits Baseline HbA1c category (≤8.0%, >8.0%) Baseline TAR
FSG	Change from baseline at Week 12 in FSG	MMRM as specified in Section 4.3.2.	 MMRM with terms for: Visits Baseline HbA1c category (≤8.0%, >8.0%) Baseline FSG
Weight	Change from baseline at Week 12 in weight	MMRM as specified in Section 4.3.2.	 MMRM with terms for: Visits Baseline HbA1c category (≤8.0%, >8.0%) Baseline weight

Table 2.	Summary	of the	analysis	of Seconda	ry Endpoints.

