# 9.3. Statistical Analyses

#### 9.3.1. General Considerations

Statistical analysis of this study will be the responsibility of Lilly or its designee.

Any change to the data analysis methods described in the protocol will require an amendment ONLY if it changes a principal feature of the protocol. Any other change to the data analysis methods described in the protocol, and the justification for making the change, will be described in the statistical analysis plan or clinical study report. Additional exploratory analyses of the data will be conducted as deemed appropriate.

All tests of treatment effects will be conducted at a 2-sided alpha level of 0.05/1-sided alpha level of 0.025, unless otherwise stated, and all confidence intervals will be given at a 2-sided 95% level.

Baseline is defined as the last non-missing measurement recorded on or before the treatment initiation visit, prior to first dose of treatment, unless otherwise specified.

Analyses will use the EAS population set to evaluate the efficacy estimand.

Summary statistics for continuous measures may include sample size, mean, standard deviation, median, minimum, and maximum. The analysis model to make comparisons within treatment relative to continuous measurements assessed over time will be an MMRM with terms for:

- visit
- country
- baseline HbA1c (≤8.0%, >8.0%), and
- baseline measurement as a covariate.

For analyses of HbA1c, continuous baseline HbA1c will be included in the model instead of baseline HbA1c category. An unstructured covariance structure will model the relationship of within-participant errors.

Summary statistics for categorical measures, including categorized continuous measures, will include sample size, frequency, and percentages. Logistic regression may be used to examine the treatment effect from baseline at 12 weeks in binary efficacy outcomes. The negative binomial regression model will be used to measure the within treatment effect of discrete count measures if deemed appropriate.

Adjustments to the planned analyses are described in the final clinical study report or in the SAP.

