When count data are presented, the percentage will be suppressed when the count is zero in order to draw attention to the non-zero counts. A row denoted "Missing" will be included in count tabulations where specified on the shells to account for dropouts and missing values. The denominator for all percentages will be the number of subjects in that treatment within the analysis set of interest, unless otherwise specified.

The analysis model to make comparisons within treatment relative to continuous measurements assessed over time will be an MMRM with terms for:

- Visits, as fixed effects
- Baseline HbA1c ($\leq 8.0\%$, > 8.0%), as a covariate
- Baseline measurement, as a covariate

For analyses of HbA1c, continuous baseline HbA1c will be included in the model instead of baseline HbA1c category. An unstructured covariance structure will model the relationship of within-participant errors.

Logistic regression may be used to examine the within-treatment effect from baseline at 12 weeks in binary efficacy outcomes. The negative binomial regression model will be used to measure the within-treatment effect of discrete count measures if deemed appropriate.

Summary of intercurrent events:

The number of participants who experience an intercurrent event will be summarized in a table by event type (treatment discontinuation for any reason, or initiation of prohibited medication) and visit. For each visit, the number of intercurrent events which happened before or during the measurements taken on that visit will be calculated, excluding the events which happened during or before the measurements taken at the previous visits.

Furthermore, the number of participants without any intercurrent events will be presented by visit too. At each visit the number and percentage of participants without intercurrent events will be shown.

All analyses will be conducted using SAS Version 9.4 or higher.

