4.3.2. Main analytical approach

The primary objective based on the efficacy estimand defined in Section 1.1 will be evaluated using the EAS dataset (Section 3). The primary analysis model for HbA1c measurements over time will be a mixed model for repeated measures (MMRM).

The observed changes in HbA1c level from baseline (Visit 2 on Week 0) to each of the scheduled post-baseline visits (Visit 3 on Week 4, Visit 4 on Week 8, and Visit 5 on Week 12) of each participant are the dependent variable. The baseline HbA1c value is incorporated as a covariate, and the visits are treated as fixed effects.

Mean change from baseline at Week 12 will be estimated by least square means (LS means), with accompanying P-value and 95% CI.

Operationally, the hypothesis defined in Section 2 will be tested at a two-sided 0.05 level by performing the test on the least square mean of changes from baseline at Week 12.

An unstructured covariance pattern will be used to estimate the variance-covariance of the withinparticipant repeated measures. Parameters will be estimated by REML with the Newton-Raphson algorithm and using the Kenward-Roger method for calculating the denominator degrees of freedom.

In case the model fails to converge, the following covariance structures will be tested in the following order:

- 1. Heterogenous Toeplitz
- 2. Heterogeneous First Order Autoregressive
- 3. Heterogeneous Compound Symmetry
- 4. Toeplitz
- 5. First Order Autoregressive, and
- 6. Compound Symmetry

The first covariance structure that converges will be used.

Missing data will not be imputed because the maximum likelihood estimate is unbiased for this model in case of a Missing at Random (MAR) mechanism. The P-value obtained for the least

square means for change from baseline will be used to determine the statistical significance to achieve the primary objective.

HbA1c values and change from baseline in HbA1c will also be summarized by visit using descriptive statistics.

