- A treatment-emergent high result is defined as a change from a value less than or equal to the high limit at baseline to a value greater than the high limit at any time during the Treatment and Follow-up periods.
- A treatment-emergent low result is defined as a change from a value greater than or equal to the low limit at baseline to a value less than the low limit at any time during the Treatment and Follow-up periods.
 - Laboratory normal ranges will be provided by the Central Lab.

An MMRM using REML model will be used to analyze the changes in lipid panel parameters from baseline to all scheduled post-baseline visits. The model will include visits and baseline HbA1c category ($\leq 8.0\%$, >8.0%) as fixed effects and baseline value of the dependent variable as a covariate.

Vital signs:

Summary tables presenting observed values and changes from baseline will be presented for vital sign data, *systolic blood pressure (mmHg), diastolic blood pressure (mmHg), pulse rate (bpm),* weight (kg), Waist Circumference measurement (cm) and BMI for participants in the Safety set. For height (cm), only observed values will be summarized at baseline.

Height and weight measurements will be used to calculate BMI, with following formula:

 $BMI = weight (kg) / [height (m)]^2$

Descriptive summaries by nominal visit will be provided for baseline and postbaseline values as well as change from baseline values. If 2 records are taken at the same visit, they will be averaged prior to being used for data summaries and analyses.

An MMRM using REML model will be used to analyze the changes in vital signs from baseline to all scheduled post-baseline visits. The model will include visits and baseline HbA1c category ($\leq 8.0\%$, >8.0%) as fixed effects and baseline value of the dependent variable as a covariate.

Counts and percentages of patients with treatment-emergent abnormal sitting systolic blood pressure (BP), sitting diastolic BP, and pulse will be presented. The criteria for identifying patients with treatment-emergent vital sign abnormalities are stated in Table 4.

Table 4.Categorical Criteria for Abnormal Treatment-Emergent Blood Pressure and
Pulse Measurement

Parameter	Low	High
Systolic BP (mm Hg) (Supine or sitting – forearm at heart level)	Observed value ≤ 90 and decrease from baseline ≥ 20	Observed value ≥ 140 and increase from baseline ≥ 20

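### The secondary, exploratory, lipid and vital-sign MMRMs adjust for HbA1c split at 8.0% but do not say how the LS mean weights the two levels

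*SAP*

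**What the plan says.** SAP 4.1 sets the general rule: "For analyses of HbA1c, continuous baseline HbA1c will be included in the model instead of baseline HbA1c category". Protocol 9.3.1 has the same rule. For all other continuous endpoints the term is the category, ≤8.0% or >8.0%. SAP 4.4.2 and its Table 2 apply this to %TAR, TAR in minutes, FSG and weight, entering the HbA1c "category as a covariate instead of continuous baseline HbA1c". Table 3 in SAP 4.5.1 applies it to the exploratory CGM measures. SAP 4.6.4.1 applies it to lipids and vital signs: "The model will include visits and baseline HbA1c category". Each of these models also holds the endpoint's own baseline value (in the protocol's words, "baseline measurement as a covariate").

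The quantity reported is defined in SAP 4.3.2: "Mean change from baseline at Week 12 will be estimated by least square means (LS means), with accompanying P-value and 95% CI". SAP 4.4.2 carries it over: "The same analytical approach will be applied for all secondary endpoints as for the primary endpoint". On software, SAP 4.1 says "All analyses will be conducted using SAS Version 9.4 or higher". Nothing states how an LS mean is averaged over the two HbA1c levels.

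The SAP also varies in what it calls the category. It is a covariate in 4.1 and 4.4.2, but a fixed effect in the composite logistic model (4.5), the lipid and vital-sign models (4.6.4.1) and the hypoglycemia models (4.6.4.2).

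**The concern.** In a randomised comparison, the weighting of a baseline factor largely cancels between arms. This trial has one arm, so the LS mean is itself the result, and any shift in it passes straight into the reported mean change and its confidence interval. The secondary questions in SAP 1.1 ask for the mean change in the study participants. An LS mean that gives the two HbA1c levels equal weight answers for a hypothetical half-and-half population.

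The cut has no design reason behind it. There is no randomisation (protocol 6.3), so 8.0% is not a stratification factor, and neither document explains it. Continuous baseline HbA1c is available and is already used in the primary model.

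A second problem follows from the same split. SAP 4.7.1 adds a subgroup term to the model and lists baseline HbA1c at 8.0% as one of the subgroups. Read together with 4.4.2, the secondary-endpoint model then contains the same two-level variable twice.

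**Working it through.** **The plan's own figure.** Protocol 9.5 and SAP 5 give n = 150, a difference of 0.3%, variability of 1.1% (taken as the SD of the change), a 1-sample t-test and two-sided alpha of 0.05. The noncentrality is 0.3 / (1.1/√150) = 3.34. Power is 91.3% from the noncentral t and 91.6% from the normal approximation, so the stated figure of at least 90% reproduces. It does not depend on this point, because the primary model uses continuous HbA1c.

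**Shift.** Let p be the share above 8.0%, m the adjusted mean change at or below 8.0%, and d the adjusted difference (above minus at or below).
- LS mean at the enrolled mix: m + p·d
- LS mean with equal weights: m + 0.5·d
- Difference: d × (0.5 − p)

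**Precision.** With residual variance s² and n participants, the enrolled-mix mean has variance s²/n. The equal-weight mean has variance ¼[s²/(np) + s²/(n(1−p))] = s²/[4np(1−p)]. The SE ratio is therefore 1/√[4p(1−p)]. It does not involve d.

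The documents give neither p nor d. The values of p below are assumed.

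| p (share >8.0%) | Shift | Variance ratio | SE ratio |
|---|---|---|---|
| 50% | 0 | 1.00 | 1.00 |
| 40% | 0.10d | 1/0.96 = 1.04 | 1.02 |
| 25% | 0.25d | 1/0.75 = 1.33 | 1.15 |
| 15% | 0.35d | 1/0.51 = 1.96 | 1.40 |

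These SE ratios are for a single post-baseline visit, before any covariate imbalance between levels. Where several visits share one category term, as for weight, the increase can be smaller, because that term is estimated from all visits together.

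**Simulation.** A Week 12 ANCOVA was run with n = 150, mean change −1.00, residual SD 1, HbA1c truncated normal on 6.5–9.0%, and correlation of 0.2 or 0.6 between HbA1c and the endpoint's baseline. All of these except n and the HbA1c limits are assumed. With an adjusted HbA1c slope of 0.2–0.4 SD:
- The continuous model and the category at the enrolled mix both returned −1.00. The continuous model had SE 0.082.
- The equal-weight LS mean was −1.07 to −1.16 (SE 0.094–0.098) with about 27% above 8.0%.
- It was −1.11 to −1.28 (SE 0.120–0.128) with about 14% above 8.0%.

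With slope 0 the equal-weight mean stayed at −1.00, but its SE was still 0.093–0.095 and 0.119–0.125 respectively.

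**Information lost by the cut.** Across four assumed distributions on 6.5–9.0%, the 8.0% indicator keeps about 50% to 72% of the variance of HbA1c. Because the endpoint's own baseline is also in the model, residual SD rose by only about 0% to 4%.

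**Duplicate term.** In the secondary models the 8.0% subgroup term is the same variable as the category already fitted. The two are aliased whether the category is a class effect or a 0/1 covariate, so separate subgroup LS means cannot be estimated from the model as written.

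**The case against.** The strongest reply is that equal weighting is not written anywhere. The sections governing the secondary endpoints (SAP 4.1 and 4.4.2) call the category a covariate, and 4.1 lists it in the same form as the continuous baseline measurement. A numeric 0/1 covariate is evaluated at its mean, which is the enrolled mix, and the shift disappears. This stands. A reader might infer that the plan prescribes 50:50 weights, but the text does not say so. The fixed-effect wording in 4.5, 4.6.4.1 and 4.6.4.2 makes the class reading likely without settling it.

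A reader might also infer that the secondary results will be flattered, on the view that change is larger above 8.0%. The documents do not support that. The sign and size of d after adjustment for the endpoint's own baseline are unknown for %TAR, FSG and weight alike. Nor is the dichotomy a serious loss of information, for the reason shown in the working.

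The rule is also prespecified. Protocol 9.3.1 uses the category for other endpoints, while for HbA1c "continuous baseline HbA1c will be included in the model instead of baseline HbA1c category". That makes the SAP consistent with the protocol on the efficacy endpoints, but it supplies no weighting. Descriptive changes by visit would let a reader notice a discrepancy. They would not correct the model-based estimate or its interval.

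**Conclusion.** The defect is an unspecified LS-mean weighting in a setting where it matters. One reading of the SAP returns the mean change of the enrolled participants. The other, which is the SAS default for a class effect, returns a 50:50 average that is also less precise unless about half exceed 8.0%. The shift is d × (0.5 − p), with size and direction unknown. The figures of 0.25d or 0.35d, and an SE higher by about 15% or 40%, rest on assumed shares of 25% or 15% above 8.0%. The precision loss does not need d to differ from zero.

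The point covers the secondary MMRMs, the exploratory MMRMs and the lipid and vital-sign MMRMs. It does not reach the primary analysis or its power. It does not reach the composite in-range endpoint, which is a logistic regression on odds. The aliasing in the 8.0% subgroup analysis of the secondary endpoints is a separate consequence of the same split, and it arises under either coding.

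**What to change.** Preferred: in the secondary, exploratory, lipid and vital-sign MMRMs, replace the category by continuous baseline HbA1c and evaluate LS means at its sample mean. With complete data this returns the enrolled mean change.

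Alternative: keep the category and state that LS means use observed margins, counting each participant once. This also gives zero shift with complete data.

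In either case, use the 8.0% cut as a grouping only in the subgroup analysis of SAP 4.7.1, and drop the duplicate category term from the secondary models there.

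The cost is one model term or one sentence, with no new data. The preferred option departs from the general model in protocol 9.3.1, so list it in SAP 4.9, which at present declares no changes. The lipid and vital-sign models need an entry there too: the model in protocol 9.3.5.3 has no HbA1c term, and the SAP adds one.
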